In case of EOT, the visit should be performed in the first day available.

Physical examination including body weight.

- Neurological examination.
- Vital signs (pulse rate, systolic and diastolic blood pressure measured after at least 5 minutes in the supine position).
- 12-lead ECG in the supine position.
- Completion of scales by rater/participant:
 - UMSARS
 - MSA-OoL
 - MoCA
 - UDRS
- Blood sampling for clinical laboratory assessments (hematology and clinical chemistry).
- Urine sampling for urine (dipstick) pregnancy test for women (only for WOCBP).
- Record concomitant medications and therapies.
- Goniometric assessment for "lateral" and "anterior" displacement
- Record AEs.
- Perform drug accountability.

The maximum amount of blood collected from each participant over the duration of the study, including any extra assessments that may be required, will not exceed 10 mL.

Repeat or unscheduled samples may be taken for safety reasons or for technical issues with the samples.

COVID-19 outbreak: in order to ensure the continuity of the study, limiting the subjects' exposure to infection and overcoming travel restriction imposed by governments, sites have been allowed:

- to perform these visits using phone call and/or video consultation
- to manage study medication return at site through a care-giver/family member
- to take Vital Sign using patient's instruments

Everything has been documented in the source data as per guidance distributed to the affected sites.

Visit 7: Telephone Follow-up

After 2 weeks from the End of Treatment, a telephone follow-up with patient should be performed, questioning about:

- Concomitant medications and therapies
- AEs

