# FIGURE 1: SCHEMA

# **TABLE 1: SCHEDULE OF ACTIVITIES**

Study Period	Screening period	Baseline		terim Vi		EOT / ET Week 12	Telephone follow-up Week 14	Notes
Day	-14 to -0	1	14±3	28 ±3	56 ±3	84 ±3	98 ±3	In the event of early termination (ET) participants should complete the End of Treatment (EoT) assessments
Visit	1	2	3*	4*	5*	6*	7	
Informed consent	X							
Eligibility criteria	X	X						
Randomization		X						
Demographics	X							
Medical history/diagnosis	X							
Prior and concomitant medications	X	X	X	X	X	X	X	Details of excluded and permitted concomitant treatments are presented in Section 6.5 of the protocol.
Vital signs	X	X	X	X	X	X		
12-lead ECG	X					X		
Physical & neurological examination	X					X		
UMSARS		X		X	X	X		
MSA-QoL		X		X	X	X		
MoCA	X					X		
UDRS		X		X	Х	Х		To be evaluated at approximately the same time of day as at the baseline visit, and this should be at least 1 hour after the patient has taken their daily dose of safinamide and is in the optimal "ON" state, where possible.
Goniometric assessment		X		X	X	X		

Study Period	Screening period	Baseline		terim Vis Veeks 2 -		EOT / ET Week 12	Telephone follow-up Week 14	Notes
Day	-14 to -0	1	14±3	28 ±3	56 ±3	84 ±3	98 ±3	In the event of early termination (ET) participants should complete the End of Treatment (EoT) assessments
Visit	1	2	3*	4*	5*	6*	7	
Haematology/Clini cal chemistry	X					Х		
Pregnancy test (urine)		X				X		Only for WOCBP.
Adverse events		X	X	X	X	Х	X	
Dispense randomized medication		X	Х	х	X			The first dose of study medication will be administered at the study centre.
Drug accountability			X	X	X	X		

Everything has been documented in the source data as per guidance distributed to the affected sites.

\*= COVID-19 outbreak: in order to ensure the continuity of the study, limiting the subjects' exposure to infection and overcoming travel restriction imposed by governments, sites have been allowed to perform these visits using phone call and/or video – consultation.

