#### 3.3.7 Study Drug Exposure and Compliance

Days of exposure to study drug will be calculated as date of last dose of study drug – date of first dose of study drug + 1. Note that the exposure calculation is intended to describe the length of time a subject was exposed to study drug and therefore does not take study drug interruptions into account. Days of exposure to study drug will be summarized by treatment with descriptive statistics and with counts and percentages of subjects with exposure in the following categories:

- <2 weeks (<14 days)
- 2 <8 weeks (14 55 days)
- 8 < 12 weeks (56 83 days)
- $\geq$ 12 weeks ( $\geq$ 84 days)

Percent compliance to the study drug regimen will be calculated as

100 x (# of tablets dispensed - # of tables returned) / # of tablets expected to be taken.

If study drug is not returned, the number of tablets returned and lost will be considered 0 for the compliance calculation. The number of tablets expected will be calculated as

- Date of last visit Date of randomization + 1, if subjects early terminated prior to Week 2 / Visit 3:
- (Date of last visit Date of Visit 3 + 1) \*2 + (Date of Visit 3 Date of randomization), if subjects early terminated prior to Week 12 / Visit 6;
- (Date of Visit 6 Date of Visit 3 + 1) \*2 + (Date of Visit 3 Date of randomization), if subjects completed the end of treatment visit (i.e., Visit 6);
- Any drug interruptions or temporary discontinuation will be taken into account.

Percent compliance to the study drug regimen will be summarized by treatment with descriptive statistics and with counts and percentages of subjects with compliance in the following categories:

- <80%
- 80-120%
- · >120%

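### For early terminators, SAP 3.3.7 counts tablets as expected up to the last visit instead of the last dose, so a participant who took every tablet until stopping can be classed as under 80% compliant

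*SAP*

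**What the plan says.** SAP 3.3.7 defines percent compliance as "100 x (# of tablets dispensed - # of tables returned) / # of tablets expected to be taken". It gives three rules for the denominator.

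- Leaving before Visit 3: "Date of last visit Date of randomization + 1, if subjects early terminated prior to Week 2 / Visit 3", at one tablet a day. The minus sign between the two dates is lost in the extracted text, and I read it as a subtraction.
- Leaving after Visit 3 but before Visit 6: the bracketed term "Date of last visit Date of Visit 3 + 1" is doubled, and the days from randomization to Visit 3 are added at one tablet a day.
- Completing Visit 6: the same as the second rule, with the Visit 6 date as the end.

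The list closes with one adjustment: "Any drug interruptions or temporary discontinuation will be taken into account". Permanent stopping is not named. For packs that do not come back, the section says "If study drug is not returned, the number of tablets returned and lost will be considered 0 for the compliance calculation".

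Exposure is handled differently in the same section: "Days of exposure to study drug will be calculated as date of last dose of study drug", less the first-dose date, plus one. Compliance is then summarized by arm, with descriptive statistics and three classes: below 80%, 80 to 120%, and above 120%.

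On the timing of the early visit, protocol section 8 (Visit 6) says "In case of EOT, the visit should be performed in the first day available" and sets no upper limit. The schedule also numbers the "Telephone follow-up Week 14" call as Visit 7.

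**The concern.** A participant who stops for intolerance has a last dose and then, possibly days later, an early-termination visit. Under both early-termination rules the days in between add to the denominator although no tablets were due. This affects someone on the full regimen who returned everything, so it is separate from dose reduction and from unreturned packs.

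Safety and tolerability is the primary objective. If more participants stop on safinamide than on placebo, the compliance table could show poorer adherence on safinamide when what happened was earlier stopping. Those are different conclusions about the drug. The arms are also small. If all 48 planned randomized participants are tabulated, 2:1 gives 32 and 16, so one reclassified participant moves the under-80% percentage by 3.1 points (1/32) or 6.25 points (1/16).

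**Working it through.** The documents state no expected-tablet total, so there is no figure of the plan's own to reproduce.

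**Inputs.** Randomization is Day 1 and Visit 3 is Day 14 (schedule of activities). The formulas and the 80% cut come from SAP 3.3.7. The gap g between last dose and last visit is an assumption, because the documents give none.

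**Expected tablets for a last visit on day L.**

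- Left before Visit 3: E(L) = L − 1 + 1 = L.
- Left after Visit 3: E(L) = 2 × (L − 14 + 1) + (14 − 1) = 2L − 13.

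Plausibility check: a nominal completer with Visit 6 on Day 84 has 2 × 84 − 13 = 155, which is 13 days at one tablet plus 71 days at two.

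**Fully adherent early stopper.** With last dose on day s and all other tablets returned, the tablets taken are E(s), and compliance is 100 × E(s) / E(s + g).

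**Gap needed to fall below 80%.** Before Visit 3, s / (s + g) < 0.8 requires g > s / 4. After Visit 3, E(s) / (E(s) + 2g) < 0.8 requires g > E(s) / 8.

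| Last dose | Tablets taken | Gap 0 | One day below threshold | Smallest gap giving <80% | Gap of 7 days |
|---|---|---|---|---|---|
| Day 7 | 7 | 100% | 1 day: 7/8 = 87.5% | 2 days: 7/9 = 77.8% | 7/14 = 50.0% |
| Day 30 | 47 | 100% | 5 days: 47/57 = 82.5% | 6 days: 47/59 = 79.7% | 47/61 = 77.0% |
| Day 45 | 77 | 100% | 9 days: 77/95 = 81.1% | 10 days: 77/97 = 79.4% | 77/91 = 84.6% |
| Day 60 | 107 | 100% | 13 days: 107/133 = 80.5% | 14 days: 107/135 = 79.3% | 107/121 = 88.4% |

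Early stops are the most sensitive. A stop on Day 7 with a visit on Day 10 gives 7/10 = 70%.

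**Opposite direction.** If the pack is not returned, the numerator rises instead. With a Day 7 stop, 14 tablets dispensed, none returned and a last visit on Day 9, compliance is 14/9 = 155.6%, in the above-120% class.

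**With the count ended at last dose.** E(s) / E(s) = 100% for every stop day and every gap, provided the unused tablets are returned.

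**The case against.** The protocol wants the early-termination visit promptly, and telephone or video contact was allowed during the COVID-19 outbreak, so gaps may be short. Stopping is also visible elsewhere: disposition with reasons (SAP 3.3.1), the exposure categories (3.3.7) and TEAEs leading to discontinuation (3.5.1). Measuring intake against the planned regimen up to the last contact is a coherent choice. The adjustment for pauses may have been meant to cover days after stopping as well.

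Much of this stands. A zero-day gap does no harm, and late stops need gaps of about two weeks. But the adjustment as written covers only pauses, no maximum gap is set, and ending exposure and compliance on different dates is neither explained nor needed.

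Several stronger readings are tempting, and the documents do not support them.

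- *Every adherent early stopper is classed below 80%.* This depends on a gap that is nowhere recorded.
- *The Visit 7 call is the last visit.* For a Day 30 stop with the call on Day 44 this would give 47/75 = 63%. However, the third rule ends completers at Visit 6 although they also have the call, drug accountability stops at Visit 6, and the call covers only medications and adverse events. The SAP does not exclude it in words, so it should be clarified, but it is not the natural reading.
- *Eight of 48 participants are at risk.* Eight is planned randomized minus planned evaluable (48 − 40). Nothing says these are people who stopped drug.
- *The 80% cut decides the per-protocol set.* The definition in SAP 3.2.4 does not mention it. The separate deviation plan is not available here.

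**Conclusion.** The point holds as a minor defect in a stated rule. Both early-termination formulas treat days after permanent discontinuation as missed doses. Compliance is therefore understated whenever the last visit falls after the last dose and unused tablets are returned. Whether the participant crosses 80% depends on the stop day and the gap: 2 days for a Day 7 stop, 6 for Day 30, 10 for Day 45 and 14 for Day 60. These thresholds assume Visit 3 on Day 14 and full intake until stopping. How many participants would be affected cannot be estimated from the documents.

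The consequence is confined to the descriptive compliance table by arm, where stopping for intolerance can look like poor adherence. No efficacy or adverse-event analysis in the SAP uses the figure.

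**What to change.** In SAP 3.3.7:

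1. In the two early-termination formulas, end the count at the date of last dose for participants with documented permanent discontinuation of study drug, and otherwise at the early-termination visit.
2. State that last visit excludes the Visit 7 telephone call.
3. State that early terminators assessed under the shared EOT/ET column follow the early-termination formulas. SAP 3.1.2 uses nominal visits, so they could otherwise be handled as having completed Visit 6.
4. Leave the third formula unchanged for Week 12 completers. Ending it at last dose would hide real non-adherence: someone who silently stops on Day 60 and attends Visit 6 on Day 84 scores 107/155 = 69% now, and would score 107/107 = 100%.

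The cost is a few lines of SAP text and a small programming change, since exposure already needs the last-dose date. There is a small downside. That date must be reliable, which may be difficult for participants lost to follow-up. An unprompted stop shortly before the early-termination visit could also be partly masked, which is why the change is limited to documented discontinuation.

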### 3.4 Efficacy Assessment

All efficacy analyses will be performed for the ITT Population. The analysis of UMSARS will be repeated for the PP Population if the number of subjects in the PP Population is less than 90% of that in the ITT Population.

#### 3.4.1 Goniometric Measurement

At each visit, the actual value of goniometric measurement (including "lateral" and "anterior" displacement) will be summarized using descriptive statistics (n, mean, standard deviation, median, minimum, and maximum).

A mixed-model repeated measures (MMRM) will be used to analyze the change in lateral displacement (and anterior displacement) from baseline. The model will include treatment, week of visit, treatment-by-visit interaction as fixed effects, and baseline score as a covariate. The unstructured covariance matrix will be assumed. Least squares means, standard errors, 95% confidence intervals and p-values for the differences between treatment groups at Weeks 4, 8 and 12 will be displayed. The treatment comparisons of most interest will be the LS means contrasts between the safinamide treated participants and the placebo treated participants at Week 12.

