9.4.2. Efficacy Analyses

The following are the efficacy endpoints for this study:

- Change from baseline to week 12 in:
 - o Goniometric measurement for "lateral" and "anterior" displacement
 - o Unified MSA Rating Scale (UMSARS) Part II
 - o MSA Health-Related Quality of Life (MSA-QoL) scale
 - o Montreal Cognitive Assessment (MoCA) scale
 - o Unified Dystonia Rating Scale (UDRS)

At each visit, the actual value and change from baseline will be summarized using descriptive statistics. Analyses of the efficacy variables will be conducted using an analysis of covariance (ANCOVA) model with study intervention included as a fixed effect and the baseline score as a covariate.

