# 2.3 Study Endpoints

#### 2.3.1 Efficacy Endpoints

Efficacy endpoints include the change from baseline to Weeks 4, 8 and 12 in the following parameters:

- Goniometric measurement for "lateral" and "anterior" displacement
- Unified MSA Rating Scale (UMSARS) Part II
- MSA Health-Related Quality of Life (MSA-QoL) scale

- Montreal Cognitive Assessment (MoCA) scale (Week 12 only)
- Unified Dystonia Rating Scale (UDRS)

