#### 3.4.2 UMSARS

UMSARS Part I total scores, Part II total scores, Part III and Part IV will be respectively summarized by treatment group over time using descriptive statistics. If any of the items is missing in Part I or Part II, then the corresponding total score is considered missing.

The MMRM analysis specified in 3.4.1 will be used to analyze the change in Part I total scores from baseline, and the change in Part II total scores from baseline, respectively.

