# 5 CHANGES FROM PROTOCOL-SPECIFIED STATISTICAL ANALYSES

The "Enrolled Population" is redefined as "Screened Population"; the "Evaluable Population" is redefined as "Intent-to-Treat (ITT)" Population".

The analyses of efficacy endpoints other than MoCA will be conducted using MMRM instead of ANCOVA.

Shift tables will not be provided for safety assessments since any abnormal findings will be captured in AEs.

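### The SAP's MMRM fits one baseline slope for all visits; a baseline-by-visit term would protect the Week 12 contrast from chance baseline imbalance at almost no cost

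*SAP*

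**What the plan says.** Protocol 9.4.2 lists change from baseline to week 12 as the efficacy endpoint and specifies an "analysis of covariance (ANCOVA) model with study intervention included as a fixed effect and the baseline score as a covariate". At Week 12 that model estimates its own baseline slope.

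SAP section 5 changes the method: "The analyses of efficacy endpoints other than MoCA will be conducted using MMRM instead of ANCOVA". SAP 3.4.1 gives the replacement: "The model will include treatment, week of visit, treatment-by-visit interaction as fixed effects, and baseline score as a covariate", and "The unstructured covariance matrix will be assumed". Its post-baseline visits are Weeks 4, 8 and 12 (SAP 2.3.1). The Week 12 contrast is singled out in 3.4.1: "The treatment comparisons of most interest will be the LS means contrasts between the safinamide treated participants" and those on placebo at that visit. Intervals and p-values are to be shown for each visit.

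The model is reused by cross-reference for UMSARS Parts I and II (3.4.2), MSA-QoL life satisfaction (3.4.3) and UDRS (3.4.5). With lateral and anterior displacement, that makes six fitted outcomes. MoCA keeps ANCOVA (3.4.4). SAP versions 1.0 and 2.0 are the same here, and neither has a baseline-by-visit term.

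**The concern.** A baseline main effect with no visit interaction assumes that change depends on baseline equally at Weeks 4, 8 and 12. The SAP neither states nor justifies this. If it fails, the pooled slope is a weighted average that can sit well away from the Week 12 slope, because the unstructured fit gives most weight to the less variable visits. Part of any chance baseline difference then stays in the Week 12 contrast, or is over-corrected.

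The trial is small and allocated 2:1, and no stratification factor is described, so baseline differences of a third of an SD will be common. At stake is how well the Week 12 estimate is adjusted for the imbalance that actually occurs.

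**Working it through.** **Inputs from the documents.** 48 randomised at 2:1, which is 32 and 16; 26 and 14 expected evaluable (SAP 2.2.3). Three post-baseline visits, unstructured covariance (SAP 2.3.1, 3.4.1). There is no stated power, effect size, SD or correlation, so the plan has no figure to reproduce.

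**Assumptions.** Baseline SD 1. Correlation of baseline with the Week 4/8/12 score varied. Visit SDs equal to baseline unless stated. First-order autoregressive residual correlation of 0.7 between adjacent visits, varied from 0.5 to 0.85.

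**Algebra (complete data).** Let d be the observed baseline difference, b_t the slope of change on baseline at visit t, and S the residual covariance.
- Week 12 ANCOVA: raw difference − b_12 × d.
- SAP model: raw difference − b_pooled × d, where b_pooled weights the visit slopes by 1'S⁻¹/(1'S⁻¹1).
- Gap between them: (b_12 − b_pooled) × d.

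The slope is b_t = r_t × SD_t/SD_0 − 1, and the residual SD is SD_t × √(1 − r_t²).

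**Likely imbalance.** SE of d = √(1/26 + 1/14) = 0.331 SD (32/16: √(1/32 + 1/16) = 0.306). An imbalance of one SE or more has about a 32% chance for any one endpoint.

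**Shift at a one-SE imbalance, 26/14, residual correlation 0.7, equal SDs.** The Week 12 SE is residual SD × 0.331.

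| Correlations | b_12 | b_pooled | Shift (SD) | Week 12 SE | Shift/SE |
|---|---|---|---|---|---|
| .80/.80/.80 | −0.20 | −0.20 | 0 | 0.199 | 0% |
| .90/.85/.80 | −0.20 | −0.121 | 0.079 × 0.331 = 0.026 | 0.199 | 13% |
| .90/.80/.70 | −0.30 | −0.118 | 0.182 × 0.331 = 0.060 | 0.237 | 26% |
| .90/.75/.60 | −0.40 | −0.107 | 0.293 × 0.331 = 0.097 | 0.265 | 37% |

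In the last row the visit weights are 1.04, −0.13 and 0.09, so the pooled slope is essentially the Week 4 slope. Over residual correlations 0.5 to 0.85, the three drifting rows span 11% to 45%.

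Simulation gives a similar range. At 32/16 with 17% dropout, the mildest drift gave 0.08 SD per SD of imbalance: 0.08 × 0.306/0.199 = 12%. At 26/14, the steepest gave 0.35 SD per SD: 0.35 × 0.331/0.267 = 43%.

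**Dependence on equal SDs (residual correlation 0.7).**
- .90/.85/.80 with visit SDs 1/1.06/1.125: slopes −0.10, −0.10, −0.10, so no shift.
- The same correlations with SDs 1/1.1/1.2: slopes −0.10, −0.065, −0.04. The Week 12 slope is now shallower than the pooled −0.095, so the sign reverses.
- .85/.75/.65: the slope gap falls from 0.165 with equal SDs to 0.065 with SDs 1/1.1/1.2.

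**Average behaviour.** Over all randomisations (600 simulated trials per case, 26/14, complete data), the SAP model's mean error was within 0.02 SD, its rejection rate was 3.7% to 5.8%, and its SD was 0% to 4% above ANCOVA's. Conditional on a 1.96-SE imbalance in the steepest case, simulated rejection was 8.7%, against 5.5% with baseline-by-visit added.

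**With the term added.** On complete data the Week 12 estimate equalled the ANCOVA estimate in every simulated trial (largest gap 2e-14). In the 32/16 simulation with dropout, the dependence on imbalance was about zero. At 26/14, the SD of the Week 12 contrast without and with the term was 0.194 and 0.195 with no drift, and fell from 0.199 to 0.194 and from 0.291 to 0.267 with drift.

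**The case against.** A baseline main effect is a legitimate MMRM specification. SAP section 5 declares the move away from ANCOVA and promises no equivalence, so failing to match the Week 12 ANCOVA is not itself a mistake. The match offered by the fix is exact only on complete data, and the plan expects 40 evaluable of 48 randomised.

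The study is an exploratory pilot with safety as its primary objective. Protocol 9.4 describes its summaries as descriptive, and no decision rule rests on a shift of this size. Protocol 4.2 argues that 12 weeks is too short for progression to confound, which fits little or no drift better than the steep case.

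All of this stands, and it limits the weight of the point. It does not justify the equal-slope assumption.

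Three stronger readings are tempting and are not supported:
- **The model biases the treatment effect or inflates type I error.** On average it does neither; the effect exists only given the imbalance observed.
- **Baseline is necessarily under-adjusted at Week 12.** A falling correlation steepens the slope only if SDs do not widen enough to offset it, and the documents are silent on both.
- **Every MMRM endpoint is affected.** An endpoint may be affected if its slope differs by visit, and nothing in the documents shows which do.

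**Conclusion.** The point holds as a cheap improvement, with moderate confidence. The text and the algebra are certain; the size is not, because every correlation and SD used here is an assumption.

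Under falling correlations with equal SDs, a one-SE baseline imbalance shifts the Week 12 difference by about 12% to 43% of its SE (closed form: 11% to 45% over the residual correlations tried). Equal slopes give no systematic shift, and widening SDs can reduce or reverse it. The plan is not invalid without the change. The added term simply removes an untested assumption from the contrast the SAP cares about most.

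**What to change.** In SAP 3.4.1, state the fixed effects as treatment, visit, treatment-by-visit, baseline and baseline-by-visit, keeping the unstructured covariance. The cross-references in 3.4.2, 3.4.3 and 3.4.5 carry the change through; 3.4.4 needs none. Add a sentence to section 5 saying that baseline adjustment is visit-specific, so that on complete data the Week 12 contrast equals the protocol's ANCOVA.

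The cost is one phrase and two extra fixed-effect parameters per model, with no material loss of precision when slopes are equal. Make the change before database lock; after that, report it as a documented deviation in the CSR, as SAP section 1 provides.
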